4.7.2 Primary Efficacy Variable – PFS

Primary Analysis on PFS

The primary variable for the assessment of efficacy is PFS, as defined in Section 3.2.1 of this SAP.

PFS based on IRR will be summarized for the ITT population using the Kaplan-Meier method. These summaries will include 1- and 2-year survival probabilities along with corresponding 95% CIs. Graphical displays (i.e. K-M plots), where appropriate, will also be produced.

Median event times and corresponding two-sided 95% CIs for the medians will be provided for PFS. A stratified log-rank test (one-sided, α =0.025) as well as hazard ratios and corresponding 95% CIs from a stratified Cox proportional hazard model, both adjusting for IMDC risk category and prior therapy, will be used to compare PFS between the two treatment arms.

When determining PFS, the recorded date of progression (defined as first time at which progression can be declared) will be used. For progression due to the presence of a new lesion, the date of progression is the first date that the new lesion was observed. If multiple assessments based on the sum of target lesion measurements are done at different times, the date of progression is the date of the last observation or radiological assessment of target lesions that shows a predefined increase in the sum of the target lesion measurements.

The robustness of the study results to the choice of baseline covariates will be investigated as described in Section 4.7.1.2. In addition, the homogeneity of the treatment effect for important subgroups will be investigated as described in Section 4.7.1.6.

A by-subject listing of the primary efficacy data will be provided.

Sensitivity Analyses on PFS

Sensitivity Analysis #1 will be done using the investigator assessment of response, adding in as events any clinical PDs specified by the investigator. A clinical PD is defined to be treatment failure not meeting the criteria for progressive disease but considered by the investigator to require removal of the subject from the study. This analysis will be conducted using the ITT and PP populations.

Sensitivity Analysis #2 will consider the initiation of new anti-tumor treatment to be an event. In this analysis, any death or PD will also be events, even those that occur after two or more missed tumor assessments. This analysis will be conducted using only the ITT population.

Sensitivity Analysis #3 will be similar to Sensitivity Analysis #2, with the addition of discontinuation of therapy considered an event as well. Again, this analysis will be conducted using only the ITT population.

Sensitivity Analysis #4 will be conducted to assess the impact of missed or not evaluable (NE) tumor assessments. This analysis will use the IRR assessments and backdate any PD events that occur immediately after missing or NE assessments. If the PD occurs immediately after NE assessment (or series of NE assessments), the PD date will be the date of the first NE assessment preceding the PD. If the PD occurs immediately after a missed assessment (or series of missed assessments), the PD date will be the date of the first missed assessment preceding the PD. This analysis will use the ITT population.

All sensitivity analyses will use the same statistical methods as the primary analysis.

Exploratory Analysis on PFS

An exploratory analysis of PFS based on IRR will be summarized for the SAF population using the Kaplan-Meier method. This analysis will examine PFS for all subjects who were randomized and administered at least one dose of the study drug. This analysis will use the same statistical methods as the primary analysis.

4.7.3 Secondary Efficacy Variables

Overall Survival

The first secondary analysis will compare OS between the two treatment arms by using a stratified log-rank test and the stratification factors included in the primary analysis. The hazard ratio for treatment will be estimated using the stratified Cox proportional hazards regression model.

Summaries showing the 1- and 2-year survival probabilities and corresponding 95% CIs will be provided along with graphical displays (similar to PFS).

Objective Response Rate

The number and proportion of subjects achieving confirmed OR (i.e. confirmed CR or confirmed PR) will be summarized and presented by treatment arm and cycle for the ITT population using a Cochran-Mantel-Haenszel (CMH) test (α =0.05) with the same stratification factors used for the PFS analysis. The odds ratio and associated 95% CI will be calculated. If the expected number in at least one cell is too small (<5), then Fisher's exact test will be used.

In addition, the BOR for each subject will be summarized (number and percentage of subjects in each category).

Duration of Response

Summaries and graphical displays for DoR will be similar to those of OS. This analysis, however, will only apply to subjects that have achieved confirmed OR.

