14.3.4 Efficacy

The primary efficacy endpoint (PFS) and secondary efficacy endpoints (OS, ORR, and DoR) analyses will be carried out using the ITT population. The primary efficacy endpoint of PFS also will be analyzed using the PP population.

Analysis of the Primary Endpoint

The primary analysis is to compare the PFS of subjects dosed with tivozanib with those subjects dosed with sorafenib. The null hypothesis is that the median tivozanib PFS is equal to that of sorafenib and the alternative hypothesis is that the two PFS medians are not equal. The IRR will be the primary data source for the PFS analysis.

The primary analysis will be carried out by using a stratified Log-Rank test, in which the stratification factors are IMDC risk category (favorable; intermediate; poor) and prior therapy (two prior VEGFR TKIs; a prior checkpoint inhibitor [PD-1 or PD1 L inhibitor] plus a prior VEGFR TKI; a prior VEGFR TKI plus any other systemic agent), and using a two-sided 5% significance level. The distribution of the PFS will be estimated using the Kaplan-Meier method. The median event time and 2-sided 95% confidence interval for the median will be also provided.

Interim Analysis

An interim analysis will be performed after 128 PFS events have been observed. The interim analysis will look into the study's futility using PFS as the efficacy evaluation endpoint. This will utilize a Lan-DeMets error spending-type function with an O'Brien-Fleming stopping boundary with an estimated two-sided beta (Type II error) of 1.2 % spent during this interim look.

The interim analysis will be performed by an independent statistician. The independent statistician will evaluate and interpret the results of the interim analysis and will provide corresponding recommendation whether to stop the study for futility or for the study to continue until end of study condition has been met.

Final analysis performed on PFS will be based on 255 events. This could be performed ≥ 6 months after the last subject is accrued. PFS interim and final analyses will be carried out by using a stratified Log-Rank test with IMDC risk category and prior therapy as stratification factors.

Handling of Missing Data

For the purpose of PFS analyses, the following steps will be considered in case of missing data:

- a) Subjects with missing imaging at baseline will be considered non-evaluable for PFS estimation and will be excluded from the PFS analyses

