4.7.1.4 Multiple Comparisons/Multiplicity

There will be no adjustment for multiplicity. PFS with one treatment contrast (tivozanib vs. sorafenib) is the only primary analysis defined for this study. The secondary analyses are simply intended to provide supportive evidence relating to the primary analysis, therefore, all efficacy endpoints will be assessed without adjustment for multiple comparisons.

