4.9 Determination of Sample Size

A sample size of 322 subjects (161 subjects per treatment arm) with a total number of 255 events will provide 90% power to detect a statistically significant difference between treatment arms with respect to PFS as assessed by the IRR. The sample size was determined based on the following assumptions:

- The distribution of the PFS for the two treatment arms will be compared by using a log-rank test with one-sided 2.5% significance level.
- The median PFS for subjects receiving sorafenib and tivozanib is 4 months and 6 months, respectively (an increase of 2 months or 50%).
- An equal number of subjects will be assigned to each treatment arm.
- Enrollment will take 15 months.
- The drop out percentage per treatment arm will be 3%.

The first secondary analysis will compare OS between sorafenib and tivozanib by using a stratified log-rank test (stratification factors included in the primary analysis), and twosided 0.8% significance level (utilizing a Lan-DeMets alpha spending function with an O'Brien Fleming boundary). The interim OS analysis will be done at the time of the final PFS analysis. Assuming a median OS for sorafenib of 12 months and a median OS for tivozanib of 16 months, 245 OS events at the time of final OS analysis and 149 OS events at the time of final PFS analysis will yield approximately 61% power to demonstrate longer OS for tivozanib using the log-rank test, given 2.5% type I error (one-sided). The final OS analysis will be performed when all subjects have been lost to follow-up, have withdrawn consent, have died, or when all subjects in follow-up have been on-study for at least 2 years, whichever occurs first.

The estimate was obtained by using East® statistical package Version 6.3 by Cytel Inc.

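### The SAP makes no multiplicity adjustment and does not gate OS or ORR on PFS, yet OS has its own 2.5% error and power and ORR its own test, so the chance of a false benefit claim across the three is not controlled

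*SAP*

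**What the plan says.** - **PFS.** SAP 4.7.2 specifies "A stratified log-rank test (one-sided, α =0.025". Protocol 14.3.4 runs the same comparison "using a two-sided 5% significance level", which is also 2.5% in the direction of benefit. SAP 4.7.1.4 names PFS as the only primary analysis.
- **OS.** SAP 4.7.3 states: "The first secondary analysis will compare OS between the two treatment arms by using a stratified log-rank test". Protocol 14.2 and SAP 4.9 give it a Lan-DeMets spending function with an O'Brien-Fleming boundary, an interim look at 149 deaths and a final look at 245. The stated power is "61% power to demonstrate longer OS for tivozanib using the log-rank test, given 2.5% type I error (one-sided". The same paragraphs quote a two-sided 0.8% level without saying which look it belongs to.
- **ORR.** SAP 4.7.3 compares the arms with a stratified CMH test at 0.05. Sidedness is not given.
- **DoR.** Protocol 14.3.4 analyzes it by the same method as PFS. The SAP states no level for it.
- **Multiplicity.** SAP 4.7.1.4 states: "There will be no adjustment for multiplicity". It adds that "The secondary analyses are simply intended to provide supportive evidence relating to the primary analysis" and that "all efficacy endpoints will be assessed without adjustment for multiple comparisons".

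No section of either document makes the OS or ORR test conditional on the PFS result.

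**The concern.** The plan treats OS in two ways. SAP 4.7.1.4 makes it background evidence for PFS. Protocol 14.2 and SAP 4.9 give it a type I error, a spending function across two looks and a power figure for showing longer survival, which is how an endpoint is set up when a claim will rest on it. The design therefore protects OS against repeated looks but not against being one of several endpoints.

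As written, a significant OS or ORR result could be declared after PFS fails, and nothing says whether that result would count. The final OS analysis comes after the PFS result is known, so a rule on what may be claimed has to be fixed beforehand. Without one, the chance of declaring some tivozanib benefit when there is none has no stated limit.

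**Working it through.** **1. Reproduce the OS design.** Inputs are from SAP 4.9: 149 and 245 deaths, medians 12 and 16 months (HR 0.75), one-sided 2.5%.

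- Information fraction: t = 149/245 = 0.608, √t = 0.780.
- O'Brien-Fleming-type spending at t: 2[1 − Φ(2.241/0.780)] = 0.00405 one-sided, or 0.81% two-sided. This matches the stated 0.8%, so 0.8% is the interim level.
- Boundaries on the Z scale: 2.648 at the interim and 1.982 at the final look.
- Mean of Z under HR 0.75: |ln 0.75| × √(149/4) = 1.756 and |ln 0.75| × √(245/4) = 2.251.
- Probability of crossing either boundary (bivariate normal, correlation 0.780): 61.0%. This matches the stated 61%.
- If 0.8% two-sided were the level for the whole OS comparison at 245 deaths, power would be only 34.4%. The 61% therefore needs the full one-sided 2.5% across both looks.

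**2. Any false benefit claim, both OS looks counted.** Assumptions: global null; PFS, OS and ORR each at 0.025 in the direction of benefit (ORR's 0.05 read as two-sided); PFS and ORR tested once, at the PFS cut.

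- Independent tests: 1 − 0.975³ = 7.31%, or 2.93 times 2.5%. The ceiling is 3 × 2.5% = 7.5%.
- The documents give no correlations, so a common value ρ is assumed. Simulation of 4,000,000 draws with the two-look OS test gives:

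| ρ | PFS or OS | PFS, OS or ORR | Ratio to 2.5% |
|---|---|---|---|
| 0 | 4.9% | 7.3% | 2.9 |
| 0.3 | 4.8% | 6.9% | 2.8 |
| 0.5 | 4.6% | 6.4% | 2.6 |
| 0.8 | 4.3% | 5.4% | 2.2 |

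PFS contributes 2.5% in every row. The chance that OS or ORR is falsely declared when PFS is not significant is therefore 7.3 − 2.5 = 4.8% at ρ = 0, falling to 5.4 − 2.5 = 2.9% at ρ = 0.8.

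**3. At the PFS data cut only.** OS is then at one-sided 0.4%. Independent tests give 1 − 0.975 × 0.996 × 0.975 = 5.3% (2.1 times). At ρ = 0.8 the figure is 4.0% (1.6 times).

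**4. Readings that raise the figure.** If ORR's 0.05 is one-sided, independent tests give 1 − 0.975² × 0.95 = 9.7%. If DoR were also tested at 0.025, they give 1 − 0.975⁴ = 9.6%.

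**5. Effect of the futility look.** At 128 PFS events and HR 4/6 the mean of Z is 0.4055 × √(128/4) = 2.294. Spending 1.2% beta puts the boundary at 2.294 − 2.257 = 0.04, so about 51% of null trials would be advised to stop. If that advice is always followed and nothing is claimed afterwards, the any-claim rate is 4.7%, 5.2%, 5.3% and 4.9% at ρ = 0, 0.3, 0.5 and 0.8 (1.9 to 2.1 times). If the two-sided wording means 0.6% is spent, about 41% would stop and the ratio is 2.0 to 2.3.

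**6. After gating.** With OS tested only when PFS is significant, and ORR either nominal or later in the same sequence, every formal claim requires PFS to succeed. The rate is then the PFS rate, 2.5%.

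**The case against.** The SAP is open about its position. It has one primary analysis, says it does not adjust, and calls the secondary endpoints supportive. On that reading only a PFS result supports a claim, and PFS is tested at 2.5% whatever happens to OS and ORR. This stands as far as it goes: the primary conclusion is not inflated. It does not explain why a purely supportive endpoint is powered and given alpha spending, and no text says that OS and ORR p-values are nominal.

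A reader might infer that the trial exceeds its stated overall error rate by a factor of about 2.6. The documents do not support that. The 2.5% is stated for PFS and separately for OS, never as a trial-wide rate. The 2.6 needs an assumed correlation of about 0.5, both OS looks and no stopping at the futility look. That look is advisory, so leaving it out is a fair worst case, but following it lowers the figure to about twice 2.5%.

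A reader might also cite the earlier Phase 3 trial in Protocol 3.6.2 as precedent. There PFS favored tivozanib (HR 0.797, p = 0.042) and OS leaned toward sorafenib (HR 1.245). That is the reverse of the case at issue: the gate would have opened and no OS benefit would have been declared, with or without it.

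**Conclusion.** The concern holds in a limited form. The plan contradicts itself on the role of OS and sets no gate, so the chance of at least one false benefit claim across PFS, OS and ORR is uncontrolled. It is about 5.4% to 7.3% over both OS looks and about 4.0% to 5.3% at the PFS cut. These figures rest on the global null, a common correlation between 0.8 and 0, ORR read as two-sided 0.05, DoR left out, and the futility advice not enforced. The inflation matters only if OS or ORR is claimed in its own right. The PFS test is unaffected. This should be corrected, but it does not threaten the primary analysis.

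**What to change.** - In SAP 4.7.1.4, replace the no-adjustment text with a gate: OS is formally tested, with its planned O'Brien-Fleming spending over both looks, only if PFS by independent review is significant at one-sided 2.5%. Otherwise OS estimates, intervals and p-values are labelled nominal.
- For ORR, either label its p-value nominal or give it a pre-stated position in the sequence. That is the sponsor's choice. Placing it behind OS could delay formal ORR testing until the final OS analysis, which may wait until all subjects in follow-up have at least 2 years on study. State the sidedness of the 0.05 in either case.
- Report DoR descriptively, without a test, because it compares responders only.
- Reconcile the supportive label in SAP 4.7.1.4 with the OS power and spending text in Protocol 14.2 and SAP 4.9, and say there that 0.8% two-sided is the level at the interim OS look.

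The cost is wording only. Sample size, PFS power and the OS spending plan do not change. The price is that no formal OS claim is possible if PFS fails, and no formal ORR claim is possible unless ORR is placed in the sequence. The 61% OS power then applies only once PFS has succeeded.

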4.8 Safety Evaluation

All safety summaries and analyses will be based upon the SAF population as defined in Section 4.4 of this SAP.

4.8.1 Extent of Exposure

Tivozanib will be administered once a day for 3 weeks, beginning on Cycle 1 Day 1 of each 4-week cycle. Sorafenib will be administered twice a day continuously, also beginning on Cycle 1 Day 1 of each 4-week cycle.

The following summaries will be produced by treatment arm:

- Number of cycles started
- Duration of treatment in days
- Total days drug was received across all cycles and for each cycle
- Total dose administered in mg across all cycles and for each cycle
- ADI, IDI, and RDI across all cycles and for each cycle
- Average daily dose administered in mg across all cycles and for each cycle
- Number and percentage of subjects on treatment by cycle
- Number and percentage of subjects with dose reduction, including a breakdown of reasons for dose reduction
- Number and percentage of subjects with dose interruption, including a breakdown of reasons for dose interruption

Average daily dose administered is calculated as the total dose administered divided by the total number of days on treatment. ADI, IDI, and RDI calculations were described in Section 4.6.

A by-subject listing of exposure data will also be provided.

4.8.2 Adverse Events

Adverse events will be coded by system organ class (SOC) and preferred term (PT) using the Medical Dictionary for Regulatory Activities (MedDRATM) Version 18.0 or later.

A TEAE is defined as an AE (identified by PT) that begins or that worsens in severity after at least one dose of study treatment has been administered. Treatment-related TEAEs are those with reasonable causality to study drug marked as "yes" on the eCRF. TEAEs with an outcome of death are those with a grade of 5 or an outcome of "fatal." TEAEs leading to treatment withdrawal are those with a study drug action taken of "drug withdrawn," while TEAEs leading to study drug dose reduction or interruption are those with a study drug action taken of "dose reduced" or "drug interruption" (respectively).

Summary tables will be presented for TEAEs by treatment arm. An overall presentation of TEAE information will include the following:

- Number and percentage of subjects with at least one TEAE
- Number and percentage of subjects with at least one TEAE of Grade 3 or higher
- Number and percentage of subjects with at least one treatment-related TEAE
- Number and percentage of subjects with at least one treatment-related TEAE of Grade 3 or higher
- Number and percentage of subjects with at least one serious TEAE

- Number and percentage of subjects with at least one treatment-related serious TEAE
- Number and percentage of subjects with at least one TEAE leading to death
- Number and percentage of subjects with at least one treatment-related TEAE leading to death
- Number and percentage of subjects with at least one TEAE leading to treatment withdrawal
- Number and percentage of subjects with at least one treatment-related TEAE leading to treatment withdrawal
- Number and percentage of subjects with at least one TEAE leading to dose reduction
- Number and percentage of subjects with at least one treatment-related TEAE leading to dose reduction
- Number and percentage of subjects with at least one TEAE leading to dose interruption
- Number and percentage of subjects with at least one treatment-related TEAE leading to dose interruption

TEAE information will also be presented by NCI CTCAE severity grade and by relationship to study treatment. If a subject had more than one occurrence of a TEAE, the most severe grade will be used in the summary tables.

The following summaries will be provided:

- Number and percentage of subjects for each TEAE, categorized by SOC and PT
- Number and percentage of subjects for each TEAE of Grade 3 or higher, categorized by SOC and PT
- Number and percentage of subjects for each TEAE, categorized by SOC, PT, and maximum CTCAE grade
- Number and percentage of subjects for each TEAE, categorized by SOC, PT, and relationship to study drug
- Number and percentage of subjects for each treatment-related TEAE, categorized by SOC and PT
- Number and percentage of subjects for each treatment-related TEAE of Grade 3 or higher, categorized by SOC and PT
- Number and percentage of subjects for each treatment-related TEAE, categorized by SOC, PT, and maximum CTCAE grade
- Number and percentage of subjects for each treatment-related TEAE leading to treatment withdrawal, categorized by SOC and PT

Counts will be by subject, not by event, and subjects are only counted once within each SOC or PT. For tables categorized by maximum CTCAE grade, subjects with multiple events within a particular SOC or PT will be counted under the category of their most severe event within that SOC or PT.

Exposure-adjusted TEAE incidence rates per 100 patient-years (p-y) may also be calculated by treatment arm for preferred terms of interest, as identified by AVEO. If requested, the exposure-adjusted incidence rate (EAIR) per 100 p-y is the number of subjects who experience a TEAE divided by the total subject exposure time multiplied by 100. For subjects who experience a TEAE, the exposure time is from the date of first dose of study treatment to the time of the first occurrence of that TEAE. For subjects who do not experience a TEAE, the exposure time is from the date of study treatment to the date of study treatment + 30 days or death date, whichever comes first.

A by-subject listing of all AEs (including non-treatment-emergent events) will be provided. This listing will be presented by treatment arm and will include: center, subject identifier, age, gender, race, adverse event (SOC, PT, and verbatim term), date of onset, date of resolution, duration, CTCAE grade, seriousness, action taken, outcome, and relatedness. The following AE listings will also be provided using a similar layout:

- Subjects who died during the study
- Subjects with treatment-emergent SAEs
- Subjects with treatment withdrawal due to TEAEs
- Subjects with dose reduction due to TEAEs
- Subjects with dose interruption due to TEAEs

For missing or partially missing dates, imputation will be done according to Section 4.7.1.3. In general, however, adverse events will be assumed to be treatment-emergent unless there is clear evidence (through comparison of partial dates) to suggest that the adverse event started prior to the date of first dose of study treatment or more than 30 days after the date of last dose of study treatment.

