Subjects with documented stable disease or an objective response may continue to receive therapy at the same dose and schedule until disease progression or unacceptable toxicities occur, or if other withdrawal criteria are met. Regardless of the duration of the study treatment, all subjects who develop early progressive disease (PD) per RECIST Version 1.1[2] prior to response evaluation will be considered to have progressed on study. Once discontinued, all subjects are to be followed for evidence of delayed effects of study drug for a minimum of 30 days from the last dose of study drug. After the 30-Day Follow-up visit, subjects will be contacted once every 3 months by the sites to collect long-term survival data. Additional contacts may be made to support key analyses, such as the analysis of overall survival at the time of the final PFS analysis, and the final analysis of OS.

Subjects experiencing unacceptable toxicities will be discontinued from further study treatment. Subjects with radiological evidence of progressive disease (per RECIST Version 1.1) per investigator/local radiology assessment should continue treatment until progressive disease is verified by an independent radiologist. An independent safety monitoring committee (SMC) will monitor the safety data from this study on a periodic basis.

Safety assessments are performed on an ongoing basis. The following procedures and evaluations can be collected at unscheduled visits as needed: electrocardiogram (ECG), physical examination, Eastern Cooperative Oncology Group (ECOG) performance status, hematology, serum chemistry, coagulation parameters, thyroid function tests, urinalysis, pregnancy tests, vital signs, tumor assessment, and survival status. Data from unscheduled assessments of the safety endpoints listed above will be included in data listings but not table summaries. For a complete schedule of planned assessments, please refer to Table 1 and/or Section 7 of the study protocol.

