3.2.2 Safety Variables

Safety endpoints include study drug exposure, adverse events, laboratory parameters, vital signs, electrocardiogram (ECG), ECOG performance status, concomitant medications, and physical examination.

Study Drug Exposure

Duration of treatment (i.e. exposure) for both tivozanib and sorafenib is defined as the time from the date of the first dose of study treatment to the date of the last dose of study treatment. Duration of treatment is calculated as: (last dose date – first dose date) + 1.

Adverse Event (AE)

Information regarding the occurrence of AEs will be collected throughout participation in this study, starting from the time the subject signs the informed consent form until a period of 30 days after the last dose of study drug. AEs will be coded by system organ class (SOC) and preferred term (PT) using the Medical Dictionary for Regulatory Activities (MedDRATM) Dictionary (Version 18.0 or later). Severity will be graded according to the National Cancer Institute (NCI) Common Terminology Criteria for Adverse Events (CTCAE) Version 4.03. AEs leading to death or study treatment discontinuation, treatment-related AEs, serious adverse events (SAEs), and treatmentemergent adverse events (TEAEs) will be considered with special attention.

A TEAE is defined as an AE (identified by PT) that begins or that worsens in severity after at least one dose of study treatment has been administered. That is, an AE is considered treatment-emergent if either of the following is met:

- The event begins on or after the first day of study treatment and before 30 days after the last dose of study treatment plus it was never recorded prior to the start of study treatment
- The event was recorded or began prior to the start of study treatment but increased in NCI CTCAE v4.03 grade on or after the first dose of study treatment

Laboratory Parameters

The following laboratory parameters will be collected in accordance with the schedule of assessments as specified in Table 1 of the study protocol:

- Hematology: complete blood count with differential and platelet count
- Serum Chemistry: sodium, potassium, chloride, bicarbonate (optional), blood urea nitrogen (BUN), creatinine, glucose, total bilirubin, direct bilirubin, aspartate aminotransferase (AST), alanine aminotransferase (ALT), lactase dehydrogenase (LDH), alkaline phosphatase, calcium, magnesium, phosphorus, albumin, amylase, lipase, and total protein

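### SAP 4.8.2: read literally, the exposure-adjusted incidence rate gives event-free subjects at most 30 days of exposure, so it would not adjust for exposure

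*SAP*

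**What the plan says.** SAP 4.8.2 (Adverse Events) states that exposure-adjusted rates per 100 patient-years "may also be calculated by treatment arm for preferred terms of interest", the terms being chosen by the sponsor. If requested, the rate "is the number of subjects who experience a TEAE divided by the total subject exposure time multiplied by 100". Two sentences then define exposure time:

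- Subjects with the event: "the exposure time is from the date of first dose of study treatment to the time of the first occurrence of that TEAE".
- Subjects without the event: "the exposure time is from the date of study treatment to the date of study treatment + 30 days or death date", whichever is first.

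Other parts of the SAP tie the safety window to the last dose:

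- 3.2.2, TEAE definition: "The event begins on or after the first day of study treatment and before 30 days after the last dose of study treatment".
- 4.8.2, rule for missing or partial AE dates: an event is taken as not treatment-emergent if it clearly began before first dose or "more than 30 days after the date of last dose of study treatment".
- 3.2.2, study drug exposure: "Duration of treatment is calculated as: (last dose date – first dose date) + 1".

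**The concern.** The sentence for event-free subjects names neither first nor last dose. It uses one undefined date for both start and end, so the interval it describes is 30 days, or less if the subject dies sooner. Two mismatches follow.

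1. Within the denominator, a subject whose first event comes at month 5 contributes five months, while an event-free subject treated for a year contributes 30 days.
2. Between numerator and denominator, events are collected over the whole treatment period plus 30 days, but event-free time stops counting at 30 days.

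The rate exists to allow for unequal time on drug between arms. Unequal time is the planned scenario: the sizing assumes longer PFS on tivozanib, and subjects with locally assessed progression "should continue treatment until progressive disease is verified by an independent radiologist". A rate that ignores time on drug would still be labelled exposure-adjusted in a report.

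**Working it through.** **No figure to reproduce.** The documents state no exposure-adjusted rate, event hazard or treatment duration for this trial. Everything below is conditional on stated assumptions.

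**Inputs**
- Treatment duration D: assumed exponential, with the SAP 4.9 PFS medians (sorafenib 4, tivozanib 6 months) as proxy. These medians do match the sizing: 4 × (1.960 + 1.282)² / (ln 1.5)² gives 256 events, against the stated 255.
- Event hazard λ: assumed constant and equal in both arms, over a wide range.
- Deaths that shorten follow-up: ignored.

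**Formulas.** Let μ = ln 2 / median and a = 30 days = 0.986 month.
- Probability of no event by D + 30 days: S = exp(−λa) × μ/(μ + λ). Let P = 1 − S.
- Mean exposure with event-free subjects followed to last dose + 30 days: P/λ. The rate is then P/(P/λ) = λ, the true value.
- Mean exposure under the literal rule: event-free subjects lose all but 30 days, so it is P/λ − S/(μ + λ).
- Inflation = 1 / {1 − λS/[P(μ + λ)]}.

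**Worked case, λ = 0.05 per month (true rate 60 per 100 p-y)**
- Tivozanib: μ = 0.1155, S = 0.6644, P = 0.3356. Inflation = 1/(1 − 0.598) = 2.49; literal rate 149.
- Sorafenib: μ = 0.1733, S = 0.7388, P = 0.2612. Inflation = 1/(1 − 0.633) = 2.73; literal rate 164.
- Literal ratio, tivozanib to sorafenib: 0.91.

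**Rare-event limit.** Inflation tends to (mean D + 30)/30.
- Sorafenib: (175.6 + 30)/30 = 6.9.
- Tivozanib: (263.5 + 30)/30 = 9.8.
- Ratio of the two: 9.78/6.85 = 1.43.

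**Range of constant hazards (true ratio 1.00 throughout)**

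| True rate per 100 p-y | Incidence, sorafenib / tivozanib | Inflation, sorafenib / tivozanib | Literal ratio, tivozanib to sorafenib |
|---|---|---|---|
| 2 | 1% / 2% | 6.4 / 8.6 | 1.34 |
| 12 (0.01 per month) | 6% / 9% | 5.0 / 5.5 | 1.10 |
| 24 (0.02 per month) | 12% / 16% | 4.0 / 4.0 | 1.00 |
| 60 (0.05 per month) | 26% / 34% | 2.7 / 2.5 | 0.91 |
| 100 | 38% / 46% | 2.1 / 1.9 | 0.90 |
| 400 | 75% / 81% | 1.3 / 1.2 | 0.94 |

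With equal durations in both arms the literal ratio is 1.00. A true ratio of 0.70 (14 against 20 per 100 p-y) appears as 0.84.

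**Early-onset events** (simulated; onset mean 30 days in 2% to 80% of subjects, the same share in each arm). The literal ratio is 0.99 to 1.02. With exposure counted to last dose + 30 days it is 0.71 to 0.79.

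**Small example.** 161 per arm, 16 events at day 60 in each arm.
- Literal, both arms: 16 × 60 + 145 × 30 = 5,310 days, or 110.1 per 100 p-y.
- To last dose + 30 days, sorafenib: 16 × 60 + 145 × 205.6 = 30,772 days, or 19.0.
- To last dose + 30 days, tivozanib: 16 × 60 + 145 × 293.5 = 43,518 days, or 13.4.

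The crude proportions are equal here and so are the literal rates: the literal rule has made no allowance for time on drug.

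**The case against.** - **The intent is plain.** The other safety windows cited end 30 days after last dose, and the preceding sentence starts at first dose. A fixed 30-day exposure would defeat the purpose of the rate, and a careful programmer would probably query it. This stands as a diagnosis: *first dose* and *last dose* were most likely left out. It does not remove the need to correct the sentence, which is the only specification of event-free exposure if the rate is requested.
- **Words may have been lost in conversion of the SAP text.** Section 4.6 is visibly damaged in this way. The sentence at issue reads as complete, but the signed SAP should be checked first.
- **Little depends on it.** The rate is optional and supportive. No hypothesis test or stopping rule uses it, the committed TEAE tables are counts and percentages, and 4.8.1 reports exposure by arm separately. This stands and limits the severity.
- **A reader might infer that the rule always inflates rates several-fold and creates a false difference between arms, for example an excess on sorafenib.** The documents do not support that. They give no event rates or treatment durations; under the assumed model the inflation fades for common events, and the false ratio changes direction and passes through 1.00.

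**Conclusion.** The point holds as a defect in the definition of an analysis rule, of minor severity. On its literal reading, the exposure-adjusted rate would not adjust for exposure.

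Under the assumptions above, inflation is about 7-fold (sorafenib) to 10-fold (tivozanib) in the rare-event limit, 2.5- to 2.7-fold at 0.05 per month, and 2-fold or less for very common events. Distortion of the arm comparison is possible but not general. It needs unequal treatment durations, and a true ratio of 1 could then appear as about 0.90 to 1.43 or be unchanged. For early-onset events the fault is the opposite of a false difference: the literal ratio stays near 1.0 where the properly computed one is 0.71 to 0.79.

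These sizes rest on PFS medians standing in for time on drug, which ignores stopping for toxicity, and on assumed event rates. That the wording is a slip rather than a deliberate 30-day rule is likely but not stated.

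**What to change.** After checking the signed SAP, replace the second exposure sentence in 4.8.2 with: *For subjects without the TEAE, exposure time runs from the date of first dose to the earliest of the date of last dose plus 30 days, the date of death, and the data cut-off date.*

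This matches the TEAE window in 3.2.2 and the date rule in 4.8.2. The cut-off term covers subjects still on treatment at the date set in SAP 4.10 (04 October 2018). The cost is one SAP sentence; the dates are already needed for the treatment-duration, survival and data cut-off definitions, so no new data are required.
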